To be specific, young and middle-aged CRC patients (18 - 60 years) experienced higher occurrence rates for almost 50% of the symptoms due to their receipt of more intensive, shorter-cycle chemotherapy regimens, lower baseline functional status, and the emergence of unique chemotherapy-toxicity symptom clusters (Morse et al., 2024). Young and middle-aged cancer survivors (age < 60) with two or more comorbid conditions are more likely to have more and severe physical or emotional symptom (Jeon et al., 2019). In addition, compared to older patients, young and middle-aged patients are more likely to be exposed to complex social factors, such as financial stress and social isolation, following a cancer diagnosis. Specifically, the treatment of cancer will affect their work and thus cause severe economic toxicity (Alsakarneh et al., 2024; Ghazal et al., 2023); Social isolation is more common in young and middle-aged patients because cancer affects their careers and relationship (Fletcher et al., 2024; Khoo et al., 2022); For patients of childbearing age, the impact of cancer on their fertility is an even more specific negative factor in leading to a bad outcome (Baronas et al., 2024; Patel & Ahnen, 2018). Specifically for young and middle-aged CRC patients in China, studies have shown that they struggle to rebuild their social support networks and to access and screen

relevant health information, so that their health needs span the entire disease journey (Yajuan et al., 2024). In addition, CRC survivors frequently experience anxiety about treatment outcomes, future prognosis, and long-term survival, with emotional or psychological support and reassurance, information about managing illness and side effects, fear of cancer recurrence, and help with sexuality problems identified as their top unmet needs (Luo et al., 2024; Ng et al., 2019). Therefore, under such complex and numerous psychological and social challenges, resilience plays an important role in helping patients to cope well with the difficulties associated with cancer. Currently, few programs exist to enhance resilience in young and middle-aged colorectal cancer survivors after they finish primary treatment, even though they have distinct challenges. Developing tailored resilience-building interventions for this group will not only support their immediate well-being but also help them maintain better health as they age, thereby meeting their long-term medical and care needs.

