In summary, for young and middle-aged CRC patients, there are more key emotional and social factors challenges whether they arise from the disease, treatment outcomes, family responsibilities, career disruption or socialization. In this context, improving patient resilience can help them adapt to these stressors, maintain mental health, and recover from emotional setbacks. Although emotional methods have been available in existing research as effective and adaptive interventions to improve patient resilience (Casellas-Grau et al., 2014; Ding et al.,

2024; Polizzi & Lynn, 2021), so far there are no studies targeting on what and how effective of these emotional strategies adopted by the patients. Emotional granularity contributes to this process by enabling patients to recognize specific emotional experiences, which in turn enables them to more effectively apply targeted emotion regulation strategies. Therefore, we hypothesized that by increasing emotional granularity in young and middle-aged CRC patients, patients could use emotion regulation strategies more effectively in the face of the emotional complexity of the cancer journey, thereby improving patient resilience and promoting overall health as well as quality of survival.

Methods

1. Aim

To clarify the relationship between emotional granularity and resilience, explore young and middle-aged CRC patients' emotional challenges and investigate how resilient patients leverage emotional granularity to support adaptive emotion regulation strategies, as well as examine patients' perspectives on interventions development.

2. Study design

This study was designed as a sequential mixed-method study that first collects and analyses quantitative data and then qualitative data to explain or generalize quantitative data (Creswell & Clark, 2017). The study will include two-phases, including quantitative phase to explore the association among emotional granularity, emotional regulation and reliance in young and middle-aged CRC survivors, then a qualitative phase to further elucidate the findings from the quantitative phase and delve deeper into the emotional challenges faced by young and middle-aged CRC patients, as well as their perspectives on AI-integrated emotional interventions.

3. Participants

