The research design for the first quantitative phase is a cross-sectional, anonymous survey. young and middle-aged CRC patients will be recruited consecutively from Chinese medical institutions in Suzhou, Jiangsu Province. Potentially eligible participants will be identified from electronic medical records in accordance with the hospital's strict data security policies. The inclusion criteria are (1) young and middle-aged adult patients (age in the range of 18-60 years); (2) patients diagnosed with CRC; (3) patients have completed primary treatments (e.g., surgery, chemotherapy, and/or radiotherapy) without experiencing a recurrence of CRC; and (4) patients

able to use a smartphone and agree to participate in the study. The exclusion criteria are (1) patients who have not been informed of their cancer diagnosis due to family decision to withhold information; and (2) patients suffering from severe conditions that may affect participation or assessment, such as significant cognitive impairment, psychiatric disorders, or communication disorder. Before the survey, patients are required to sign an informed consent form. Regarding the sample size, Monte Carlo simulation for mediation analysis will be used (Donnelly et al., 2023; Fritz & MacKinnon, 2007). We will begin by specifying our population parameters based on the smallest effect size of interest (SESOI). In our mediation model, the following paths were defined: Path a is the effect of emotional granularity on emotional regulation. Path b is the effect of emotional coping on resilience (while controlling for emotional granularity). Path c is the direct effect of emotional granularity on resilience after accounting for the mediator (Figure 4). standardize example value of $a=0.5$, $b=0.4$ (Donnelly et al., 2023). 200 participants will reliably ensure at least 80% power. Moreover, considering a 15% attrition rate, the sample size should be 236 at least.

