Appendix

1. Emotion-resilience assessment questionnaire for young and middle-aged colorectal cancer patients (Chinese version)

第一部分：一般资料调查表

- *住院号（即患者唯一编号）:
- *年龄: _____ 岁
- *性别: 男 女
- *就业状态: 在职 学生 离/退休 待业 失业/无业
- *婚姻状态: 已婚 未婚 离异 丧偶
- *结直肠癌家族史: ①有 ②无
- *其他疾病: ①无 ②糖尿病 ③高血压 ④心脏病 ⑤其他_____
- *肿瘤位置: 结肠 直肠 结直肠 其他_____
- *结直肠癌 TNM 分期: T_N_M_
- *是否有造口: ①无
②有（结肠造口 回肠造口； 造口时间: _____年_____月_____日）
- *是否转移: _____（如是，请填写转移部位）
- *所接受过的治疗（可多选，请在横线上写出治疗开始和结束日期）:
手术_____ 化疗_____（请标注化疗方案）
放疗_____ 靶向_____ 免疫_____ 其他_____

13. *最后一次接受主要治疗的日期: ____年____月____日

14. *目前所遗留的肿瘤/造口相关并发症:

肿瘤/术后相关并发症	造口相关并发症	其他 (请详细填写)
 无	 无	
 低前切除综合征	 造口渗漏	
 肠道功能障碍	 腹旁疝	
 肠道梗阻	 周围皮肤并发症	
 吻合口狭窄	 造口脱垂	
 吻合口瘘	 造口狭窄	
 局部复发及相关并发症	 造口回缩	
 肿瘤复发/转移	 高排出造口	
	 造口梗阻	
	 感染与出血	

个人情况调查表

1. 家庭人均月收入 (元): <3000 3001~6000 6001~9000 >9000
2. 居住地: 城镇 农村
3. 付费方式: 全公费 城镇基本医疗保险 新型农村合作医疗
 商业医疗保险 其他社会保险 贫困救助 全自费
 其他 _____ (请具体填写)

第二部分 RDEES

请你仔细阅读每一项题目，在每一题后最符合自己情况的数字上画圈 “○”

1 表示“这完全不是对我的描述”。5 表示“这是对我的精准描述”。

题目	符合程度				
	1	2	3	4	5
1. 我知晓特定情绪的不同差异	1	2	3	4	5
2. 我一生中已体验到各种各样的情绪	1	2	3	4	5
3. 每种情绪对我而言都有着特殊涵义	1	2	3	4	5
4. 我能领悟到类似情绪之间的细微差异 (如沮丧和抑郁; 生气和恼怒)	1	2	3	4	5
5. 我情感丰富	1	2	3	4	5
6. 我知道每种情绪都蕴含着完全不同的意义	1	2	3	4	5
7. 在日常生活中, 我并没有体会到纷繁复杂的情绪	1	2	3	4	5
8. 如果用颜色来形容不同的情绪, 我可以注意到每一种颜色 (情绪) 之间的细微差别	1	2	3	4	5
9. 我能够意识到自身各种情绪感受之间的细微差别	1	2	3	4	5
10. 我倾向于体验到各种不同的情绪感受	1	2	3	4	5
11. 我擅长区分那些意思紧密关联的情绪词间的细微差异	1	2	3	4	5

第三部分 DERS

指导语：下面的量表用于评估您的情绪调节，每个问题有 5 种不同答案可供选择，请根据您最近的实际情绪调节体验实际情况，选择相应的答案打勾 “√”。

	从不	偶尔	有时	经常	总是
1. 我明白我的感受					
2. 我会注意我的感受是怎样的					
3. 我有过情绪极为强烈和情绪失控的经历					
4. 我不清楚自己的感受是怎样的					
5. 我很难弄明白自己的感受					
6. 我会留意自己的感受					
7. 我能清楚地知道自己的感受是怎样的					
8. 我在意我感受到什么					
9. 我对于自己的感受如何感到困惑					
10. 当心烦意乱时，我能觉察我有这个情绪					
11. 当心烦意乱时，我为有这种情绪而生自己的气					
12. 当心烦意乱时，我为有这种情绪而感到尴尬难堪					
13. 当心烦意乱时，我难以把事情（任务）完成					
14. 当心烦意乱时，我会变得失控					
15. 当心烦意乱时，我相信我会一直处于这种状态很长时间					
16. 当心烦意乱时，我相信最后我会感到相当抑郁					
17. 当心烦意乱时，我相信我的感觉是有根据和重要的					
18. 当心烦意乱时，我难以专注在其他事上。					
19. 当心烦意乱时，我感到失控					
20. 当心烦意乱时，我仍然能把事情做完					
21. 当心烦意乱时，我为自己有这种感受而感到羞愧。					
22. 当心烦意乱时，我知道我能够找到方法让自己最后的感觉好一些					
23. 当心烦意乱时，我觉得好像自己是软弱的。					

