24. 当心烦意乱时，我觉得我好像仍能控制自己的行为。					
25. 当心烦意乱时，我对于自己有这样的感受感到内疚。					
26. 当心烦意乱时，我难以集中注意力					
27. 当心烦意乱时，我难以控制自己的行为					
28. 当心烦意乱时，我相信无论做什么都不能使自己感受好一些。					
29. 当心烦意乱时，我对于自己有这种的感受而感到恼火。					
30. 当心烦意乱时，我开始感到自己非常差劲。					
31. 当心烦意乱时，我相信能做的只有任自己陷在这种情绪中。					
32. 当心烦意乱时，我会最自己的行为失去控制。					

33. 当心烦意乱时，我难以考虑其他的任何事情。					
34. 当心烦意乱时，我会花时间去弄清楚自己真正的感受是什么					
35. 当心烦意乱时，我需要长时间才能够感觉好些					
36. 当心烦意乱时，我感到情绪极其强烈难以抵抗					

第四部分 CD-RISC-10

指导语：请根据您在最近一个月在遇到问题或挑战时的实际感受，在最符合该条目的答案打勾“√”。

	从不	很少	有时	经常	几乎总是
1. 当事情发生变化时，我能够适应					
2. 无论人生路途中发生任何事情，我都能处理它					
3. 面临难题时，我试着去看到事物积极的一面					
4. 历经磨难会让我更有力量					
5. 我很容易从疾病、受伤或困难中恢复过来					
6. 我相信即使遇到障碍我也能够实现我的目标					
7. 压力之下我仍然能够集中精神地思考问题					
8. 我不会轻易地被失败打倒					
9. 在处理生活中的失败和困难时，我是个坚强的人					
10. 我能够处理一些不愉快或痛苦的感觉，如悲伤、害怕和生气					

2. Individual Interview Guide for Young and Middle-Aged CRC Patients

Hello! Thank you very much for agreeing to participate in this interview.

We are conducting a study to: Explore the emotional needs of young and middle-aged colorectal cancer (CRC) patients, and how resilient patients leverage emotional granularity to support positive coping strategies. And Investigate patients' perspectives on AI-integrated emotional intervention programs, to help further development of an AI-integrated emotional intervention to enhance resilience in young and middle-aged CRC patients.

This interview will last approximately 30–60 minutes. All information is for academic research only, and you may decline to answer or stop at any time. If you have any questions, please feel free to ask before we begin. Shall we start?

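### No minimum interval after primary treatment is set, so for patients surveyed within 30 days the one-month CD-RISC-10 score partly covers the treatment period

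*Combined protocol and SAP*

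**What the plan says.** - **Eligibility (section 3, criterion 3):** "patients have completed primary treatments (e.g., surgery, chemotherapy, and/or radiotherapy) without experiencing a recurrence of CRC". No other inclusion or exclusion criterion sets a time since treatment.
- **Recruitment and design (section 3):** participants "will be recruited consecutively from Chinese medical institutions in Suzhou, Jiangsu Province", and "The research design for the first quantitative phase is a cross-sectional, anonymous survey". Each patient therefore contributes one score, at whatever time after treatment they are approached.
- **Target population:** the background says "few programs exist to enhance resilience in young and middle-aged colorectal cancer survivors after they finish primary treatment". Section 2 also describes the quantitative phase as a study of survivors.
- **Outcome recall period (Appendix 1, Part 4, CD-RISC-10):** "请根据您在最近一个月在遇到问题或挑战时的实际感受", that is, how the patient actually felt when facing problems or challenges in the most recent month. Section 4 describes the scale without mentioning this window.
- **Mediator recall period (Appendix 1, Part 3, DERS):** recent experience, with no length given.
- **Treatment date (Appendix 1, Part 1, item 13):** "最后一次接受主要治疗的日期", the date of the last primary treatment. The preceding item asks for start and end dates of each treatment.
- **Analysis (section 6.1):** a simple mediation model with a bootstrap interval. Time since treatment appears nowhere as a criterion, covariate, subgroup or sensitivity analysis.

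**The concern.** The recall window and the entry rule do not fit together. A patient surveyed soon after the last treatment is eligible, but the month being rated includes days of treatment. A patient surveyed two years later rates a month well clear of it. Both scores enter the same model and the same CDRS quartiles.

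Two things are at stake.

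- **Interpretation.** For the early patients, part of the resilience score does not describe the period after treatment that the rationale is about.
- **Bias.** If treatment temporarily worsens both DERS and CD-RISC-10, the common shift adds to the association between them. The model reads that association as path b, so the distortion favours the study hypothesis. The same shift could move recently treated patients towards the lowest quartile from which interviewees are drawn.

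**Working it through.** **The plan's own figures.** Section 3 gives 200 participants and 15% attrition: 200 / (1 - 0.15) = 235.3, rounded up to 236, as stated. A simulation with the plan's a = 0.5 and b = 0.4, two-sided 0.05, a direct path assumed between 0 and 0.3, and a joint-significance test standing in for the bootstrap gives power above 0.99 at n = 200. That agrees with the claim of at least 80%. This point disputes neither figure.

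**Overlap of the recall window.** Take one month as 30 days and let t be the days since treatment ended. The share of the window at or before the end of treatment is max(0, 1 - t/30):

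| Day surveyed | 0 | 7 | 14 | 21 | 30 or later |
|---|---|---|---|---|---|
| Share | 100% | 77% | 53% | 30% | 0% |

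**How many patients.** The documents do not say. If time since treatment is assumed uniform over 0 to T months, the share with any overlap is 1/T:

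| T (months) | 3 | 6 | 12 | 24 | 60 |
|---|---|---|---|---|---|
| Share | 33% | 17% | 8% | 4% | 2% |
| Of 200 | 67 | 33 | 17 | 8 | 3 |

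**Effect on path b.** Assume that a fraction f has both DERS and CD-RISC-10 shifted by d SD in the adverse direction, with granularity unaffected and a zero direct path. Score DERS so that higher means better regulation. The mixture adds k = f(1 - f)d² to both variances and to their covariance. The covariances are then:

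- granularity with regulation: 0.5
- granularity with resilience: 0.5 × 0.4 = 0.2
- regulation with resilience: 0.4 + k

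Path b controls for granularity, so

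b_obs = (0.4 + k - 0.5 × 0.2) / (1 + k - 0.5²) = (0.30 + k) / (0.75 + k).

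If the true b is zero, b_obs = k / (0.75 + k). Standardised path a becomes 0.5 / √(1 + k). Regulation and resilience keep equal variances, so b_obs is also the standardised value.

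| f, d | k | b, true 0.40 | b, true 0 | a, true 0.50 | a × b, true 0.20 |
|---|---|---|---|---|---|
| 0.02, 0.5 | 0.0049 | 0.404 | 0.006 | 0.499 | 0.201 |
| 0.02, 0.8 | 0.0125 | 0.410 | 0.016 | 0.497 | 0.204 |
| 0.10, 0.5 | 0.0225 | 0.417 | 0.029 | 0.494 | 0.206 |
| 0.30, 0.8 | 0.1344 | 0.491 | 0.152 | 0.469 | 0.231 |

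For scale, the standard error of b at n = 200 is about √[(1 - 0.4²) / (200 × 0.75)] = √(0.84 / 150) = 0.075. The shift in a true 0.40 is 0.017 to 0.091 over the 10-30% range and at most 0.010 at 2%.

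**Cost in power of leaving early patients out.** In the heaviest case above, 67 of 200 are removed and 133 remain. Simulated power with a = 0.5, b = 0.4 and a zero direct path is then about 0.99.

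**The case against.** A reader might infer that the outcome measures resilience during treatment instead of survivorship, and that the study fails to answer its question for recently treated patients. The documents do not support that. The window lies wholly before the end of treatment only at about day 0, is mixed up to day 29 and is clear from day 30. Nothing says that patients are recruited at discharge or at the last treatment visit. A patient just past treatment also belongs to the population named in the background.

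Further points on the other side:

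- **Construct.** The background describes resilience as a response to a difficult situation, and the CD-RISC-10 asks about problems and challenges. A month that includes treatment is not foreign to that construct. This stands, but it does not make such a month a post-treatment month.
- **Stability.** Section 4 reports test-retest values of 0.88 over four to eight weeks for the English DERS and 0.73 for the Chinese CD-RISC-10. These suggest some stability, so a shift of 0.5-0.8 SD is an assumption. They do not rule out a treatment effect, and the interview guide itself asks how emotions changed after chemotherapy and surgery.
- **Size.** The upper end is extreme. A 30% share needs time since treatment to span only about three months, and the calculation applies the full shift to everyone within 30 days although the overlap shrinks daily. The fully standardised indirect effect also moves less than path b, from 0.20 to 0.206-0.231, because standardised path a falls. All of this stands.
- **Remedy.** Distress need not end at day 30, so an interval aligns the recall window without removing every effect of recent treatment. This is a reason to adjust for time since treatment as well.

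**Conclusion.** The mismatch is real and limited. Criterion 3 allows a survey at any time after treatment, the outcome looks back one month, and no planned analysis uses the recorded treatment date. For patients surveyed within 30 days, the resilience score therefore covers a period partly (at day 0, wholly) before treatment ended.

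Its numerical effect cannot be determined from the documents. Under assumed shares of 10-30% and an assumed adverse shift of 0.5-0.8 SD on both scales, a true path b of 0.40 appears as about 0.42-0.49 and a true zero as about 0.03-0.15. The case to guard against is the upper end of the second range, where an association appears that does not exist. With a few percent affected, the distortion is negligible beside sampling error. The change is worth making because it is cheap and settles the matter whatever the share turns out to be.

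**What to change.** 1. **Eligibility.** Add to criterion 3 that the survey is completed at least one month (the CD-RISC-10 recall period) after the date in Appendix 1 item 13. Approach patients who are too early at a later visit.
2. **Patients already surveyed earlier than that.** Keep them in the main analysis. Include time since last primary treatment as a covariate in both equations of the mediation model, with its functional form stated in advance. Prespecify a sensitivity analysis that leaves out those within one month.
3. **Interview sampling.** Do not remove these patients from the quartile cut-points. They are eligible, and section 3 uses the quartiles to obtain varied perspectives.

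**Cost.** One sentence in section 3 and two in section 6.1. Recruitment slows slightly, because some patients are approached a few weeks later. The treatment date is already collected. The completion date of each questionnaire must also be available, and the form as printed in Appendix 1 shows no field for it. Under the plan's own a and b, the sensitivity analysis keeps power of about 0.99 even if a third of the 200 are left out.

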For subsequent qualitative phase, semi-structured qualitative individual interviews will be used to collect in-depth insights from young and middle-aged CRC survivors from quantitative part. According to the sample size requirements for interview in qualitative research in social sciences (Bekele & Ago, 2022), 20-25 participants will be selected based on quartiles of CDRS scores in the quantitative phase to explore common perspectives as well as emotional strategies employed by patients in different score bands to ensure that the qualitative interviews include a diverse range of perspectives, and will capture variations in emotional coping strategies and resilience.

[figure not shown]

Figure 4 Path assumption

4. Data collection for quantitative phase

Nurses or post graduate nursing students will be recruited as research assistants to support participant screening, data collection, and follow-up assessments. They will be responsible for identifying eligible participants and explaining the study procedures. After providing informed consent, participants will complete the questionnaires. For participants who have difficulty reading the written questions, the research assistants will read the questions and options verbatim without adding any interpretation. After the questionnaires are submitted, the research assistants will check them for completeness. See appendix 1 for the questionnaire used for the survey. Measurement tools used for the survey will include the following.

General Information Questionnaire

The general information questionnaire will be self-designed after literature review. The questionnaire includes age, sex, nationality, marital status, education, occupation, religious beliefs, monthly per capita household income, payment method of medical expenses, and other diseases. CRC family history, cancer types, metastasis, treatments received, stoma-related information.

The Chinese version of Range and Differentiation of Emotional Experience Scale (RDEES)

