A preliminary interview outline will be developed based on a review of relevant literature and pre-tested with three patients before finalizing the interview guide. All interviews will be conducted by postgraduate nursing students with qualitative research experience. Participants will be briefed on the purpose and procedures of the interviews before conducting the prearranged interviews in the clinic. Each individual interview lasted 30-60 minutes; the sample will be considered saturated until no new themes arose. We will conduct interviews in the following aspects. (1) Background and emotional journey; (2) Emotional needs and support; (3) Strategies of emotional regulation and improving emotional granularity; (4) Attitudes toward ai-driven tools, perceived emotional appropriateness, cultural sensitivity, accessibility barriers, and suggestions for improvement. See appendix 2 for the interview guide.

6. Data analysis

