2.3 Coping Strategies and Emotional Granularity

- What coping strategies do you typically use when feeling down or stressed?

Prompt: Can you give an example? Do these strategies differ at home, work, or in social settings?

- Do you differentiate among emotions (e.g., “anxiety,” “fear,” “worry”) and choose different strategies accordingly?

Prompt: Do you find such granularity helpful in managing your emotions? Would you like to share some ways of differentiating emotions that you have found to be effective?

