2.4 Perspectives on AI-Integrated Emotional Interventions

- If there were an AI-based tool that could identify and respond to your emotions in real time, would you be willing to try it?

Prompt: Would you prefer voice feedback, text messages, graphical reports, etc.?

- What concerns do you have about AI-driven emotional support?

Prompt: Data privacy? Technical reliability? Other issues?

- **How do you think an AI tool could best complement support provided by nurses or human caregivers?**

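### Three interview topics listed in Section 5 have no question or prompt in the guide, and the granularity items lean toward the hypothesis

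*Combined protocol and SAP*

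**What the plan says.** Section 5 (Data collection for qualitative phase) lists four areas for the interviews. The fourth covers attitudes to AI tools together with "perceived emotional appropriateness, cultural sensitivity, accessibility barriers, and suggestions for improvement". The section then refers to Appendix 2 for the guide. It also says that a preliminary outline will be "pre-tested with three patients before finalizing the interview guide". Section 3 sets the format: "semi-structured qualitative individual interviews will be used to collect in-depth insights".

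In Appendix 2, section 2.4 asks about an AI tool ("would you be willing to try it"), with a prompt on output format. It then asks an open question on concerns, with the prompt "Data privacy? Technical reliability? Other issues", and a question on how AI could complement human support. Section 2.5 asks about expectations and about what the team should attend to.

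On granularity, section 2.3 begins with an open question on coping. It next asks, in one sentence, whether the participant distinguishes emotions and picks strategies to match. Two prompts follow: "Do you find such granularity helpful in managing your emotions", and an invitation to share ways of distinguishing emotions that have worked. The introduction spoken to participants gives one study purpose as exploring "how resilient patients leverage emotional granularity to support positive coping strategies".

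**The concern.** There are two separate issues, both in Appendix 2.

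The first is coverage. The guide is the instrument that Section 5 points to, yet three topics in that section have no counterpart in it. Whether they come up would vary by participant and interviewer. If few people mention cultural fit, the team could not tell whether it is unimportant or was simply not asked about. Section 5 treats the sample as saturated when no new themes arise, and Section 6.2 builds themes from the transcripts. A topic that nobody raises yields no theme, so saturation could be declared with it unexplored. Accessibility has a further difficulty: Section 3 requires participants to be able to use a smartphone, so some of the people most likely to volunteer access problems are not in the sample.

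The second is wording. The study hypothesis, stated just before the Methods, is that greater granularity lets patients use regulation strategies more effectively and so improves resilience. The granularity items in 2.3 point the same way, and the introduction signals that direction before the first question. Section 6.3 uses the interviews to interpret how granularity and regulation relate to resilience, and plans to discuss discrepancies. If the questions make agreement the easy answer, discordant experience is less likely to reach that step.

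**Working it through.** No arithmetic beyond a count applies. The check sets Section 5 beside every question and prompt in Appendix 2, then examines the form of the granularity items.

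**Coverage of the fourth area**

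| Topic in Section 5 | Place in Appendix 2 | Named in a question or prompt? |
|---|---|---|
| Attitudes to AI tools | 2.4, willingness, concerns and complementing human support | Yes |
| Emotional appropriateness | None; nearest are output format (2.4) and interaction style (2.5) | No |
| Cultural sensitivity | None | No |
| Accessibility barriers | None; nearest are the residual item in the concerns prompt (2.4) and preferred mode of support (2.2, not about AI) | No |
| Suggestions for improvement | 2.5 | Yes |

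Five topics are listed, two have a question, and 5 - 2 = 3 have neither a question nor a prompt. The concerns question in 2.4 is open, but its two named prompts are privacy and reliability. The remaining prompt is a general residual.

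**Form of the granularity items in 2.3**

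- *Opening question on coping:* open and neutral. It does not mention granularity.
- *Main granularity question:* closed, and it joins two things, distinguishing emotions and choosing strategies accordingly. A participant who does the first but not the second has no clear answer, and a plain yes cannot be assigned to either part. The sentence also states the hypothesised link.
- *First prompt:* asks whether granularity is helpful. No is a possible answer, so it does not presuppose a benefit, but benefit is the only direction it names.
- *Second prompt:* presupposes that the participant has ways that work.
- *Introduction:* describes resilient patients as drawing on granularity for positive coping, before any question is put.

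None of the three granularity items (one question, two prompts) asks whether telling feelings apart makes no difference, is difficult, or makes things worse.

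**Whether another part of the plan closes the gap**

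- *Pre-test with three patients (Section 5):* not stated to check topic coverage or leading wording.
- *Sampling by resilience quartile (Section 3):* brings in participants with low scores, who are still asked the same items.
- *Independent double coding, member checking and reflexive notes (Section 8), and discussion of discrepancies (Section 6.3):* these work on answers already given. They cannot supply answers that were never sought.

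**The case against.** A good case can be made that this matters little. A semi-structured guide need not script every sub-topic. The open concerns question, its residual prompt, and the prompts on output format, interaction style and mode of support are natural openings for emotional fit and for barriers. Collection and analysis are iterative (Section 6.2), and the guide is not final until after the pre-test. On wording, an open coping question comes first, and participants can answer no both to the main question and to the first prompt. Asking for methods that work fits the third area in Section 5, which includes improving granularity. The introduction largely restates the aim, and Section 5 requires participants to be briefed on the purpose. The guide appears only in English while the questionnaire is in Chinese, so the spoken wording may differ.

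Much of this stands, and it rules out two stronger readings.

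A reader might infer that study aims will go unanswered. The documents do not support that. The three topics are interview topics in Section 5, not aims. The aim in Section 1 is the broader one of patients' perspectives on developing interventions, and 2.4 and 2.5 address it directly.

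A reader might also infer that only confirming answers are invited, or that the granularity theme will be biased. That is not shown either: no is an available answer, only the second prompt presupposes a benefit, and the plan intends to discuss discrepancies.

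The objection does not remove the mismatch between Section 5 and the guide or the one-directional form of the granularity items. Openings for spontaneous mention are not systematic coverage, and no stated safeguard is aimed at either problem.

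**Conclusion.** The point holds as a modest, inexpensive improvement. Three of the five topics in the fourth area have no question or prompt in Appendix 2, so data on them would depend on spontaneous mention and their absence could not be interpreted. The granularity items carry a risk of acquiescence in the theme that feeds the integration in Section 6.3. The size of that risk cannot be estimated from the documents, and no bias has been demonstrated.

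This rests on two assumptions: that interviewers follow the guide broadly as printed, and that the version spoken to participants matches the English text. If interviewers already probe the three topics routinely, or the Chinese wording is neutral, the corresponding part falls away. The documents state neither.

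**What to change.** Revise Appendix 2 before the guide is finalised, ideally before the three-patient pre-test so that the new wording is tried out.

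1. **Section 2.4:** add one open prompt for each missing topic, for example: *When would a response from such a tool feel emotionally right or wrong to you? How well would it fit your family and cultural habits? What would make it hard for you to use?*
2. **Section 2.3:** split the granularity question and reword it and its prompts openly, for example: *How, if at all, do you tell similar feelings apart?* and then *What difference, if any, does that make to what you do: for better, for worse, or none?* Ways that have helped can still be asked about afterwards, of participants who report some.
3. **Introduction:** replace the clause on resilient patients with a neutral purpose statement, such as learning how patients experience and handle their emotions. Deleting it outright would cut the briefing on purpose that Section 5 requires.
4. **Pre-test:** state that it checks topic coverage and leading wording, in the language used with participants.

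If interviews have already begun, the iterative collection in Section 6.2 allows the changes to be made, with the date of change recorded so that earlier interviews can be read accordingly. The cost is a few lines of text and a few more minutes within the 30-60 minute interview.
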